8.4.1.2. Adverse Event Intensity

The unmasked treating investigator / masked Investigator shall assess and record the intensity of the (S)AE according to the following scale:

- Mild (awareness of sign or symptom, but easily tolerated)
- Moderate (discomfort sufficient to cause interference with normal activities)
- Severe (incapacitating, with inability to perform normal activities)

An AE that is assessed as 'Severe' should not be confused with an SAE. 'Severe' is part of a scale used for rating the intensity of an event. An event is defined as 'Serious' when it meets 1 of the pre-defined outcomes as described in [Section 8.3.2](#). A severe AE can be of relatively minor medical significance / non-serious (*e.g.* severe itching). Similarly, an SAE can be of mild intensity (*e.g.* mild chest pain).

For AEs that change in intensity, the start and stop date of each intensity should be recorded.

8.4.1.3. Adverse Event Outcome

At the time of reporting the outcome of an AE, it must be recorded as ongoing, resolved, or resolved with sequelae / death.

8.4.1.4. Adverse Event Follow-Up

Non-Serious Adverse Events

The masked Investigator will follow subjects from the study who are withdrawn from the study as a result of an AE until the event has resolved, subsided, stabilised, or until the event is otherwise explained, or the subject is lost to follow-up.

Other AEs will be followed until the subject has recovered or the subject's participation in the study is complete.

Serious Adverse Events

The Sponsor or delegated Pharmacovigilance Service Provider will follow-up SAE reports to completion. Investigators are expected to provide the additional information required for complete assessment and documentation of the SAE reports in a timely manner.

When more information becomes available, the masked Investigator must update the SAE Form in the subject's eCRF. The eCRF system will automatically send the follow-up report to the Sponsor for processing.

If the eCRF system cannot be used for any reason, the Investigator shall submit the follow-up report by email or fax to the Sponsor (email: [contact]; fax: [name]), within the same timeframe. The data should be entered in the eCRF as soon as the system becomes available again.

Copies of hospital reports, autopsy reports and other documents should be provided if they are relevant to the evaluation of the SAE.

SAEs should be followed-up until the event has resolved, subsided, stabilised, or until the event is otherwise explained, or the subject is lost to follow-up.

If the Investigator learns of any SAE at any time after a subject has completed the study, and he / she considers the event to be possibly related to the study drug or the injection procedure, he / she will notify the Sponsor by emailing or by faxing (email: [contact]; fax: [name]).

Screening Failures

For screening failures, only (S)AEs related to participation at the screening visit will be followed-up as described in the sections above.

8.4.2. Pregnancy / Prenatal Exposure

Pregnancies will be recorded from the time of providing consent until the end of the study (Visit 11 – Month 24 / Exit Visit).

Subjects with reproductive potential, whether male or female, must agree to use contraception for the duration of the study. The Investigator should counsel subjects with regard to the possible untoward effects on the foetus.

Female subjects of childbearing potential will need to have a negative pregnancy test at Visit 1 (Screening) and at Visit 2 (Day 0). In addition, a urine pregnancy test will be taken at each repeat injection visit and for any woman of childbearing potential who missed 1 period at any time during the study. Female subjects who are pregnant at the time of repeat injection must not receive further injection(s). Pregnant subjects should not be withdrawn from the study, but should be asked to continue with all scheduled study visits and procedures until the end of the study to ensure complete follow-up.

Pregnancy occurring in a female subject or in the partner of a male subject should be reported immediately to the Investigator. The Investigator should report pregnancies immediately to the Sponsor by using the Pregnancy / Prenatal Exposure Form in the eCRF (for study subjects) or via email or fax (email: [contact]; fax: [name]) (for

pregnant partners). The eCRF system will automatically send the form to the Sponsor for processing. If the eCRF system cannot be used for any reason, the Investigator shall submit the Pregnancy / Prenatal Exposure report by email or fax to the Sponsor (email: [contact]; fax: [name]). The data should be entered in the eCRF as soon as the system becomes available again.

In case of a pregnancy in the partner of a male subject, the Investigator should obtain written informed consent from the pregnant partner prior to obtaining information about the pregnancy. The Investigator will provide the pregnant partner with a copy of the Pregnant Partner Information Sheet / Informed Consent Form.

Pregnancies should be monitored until conclusion. The outcome of all pregnancies (spontaneous miscarriage, elective termination, normal birth or congenital abnormality) must be followed up and documented via the Pregnancy Follow-up Form, even for subjects withdrawn from the study or who completed the study.

Pregnancy in itself is not regarded as an AE unless there is a suspicion that the study drug may have interfered with the effectiveness of a contraceptive medication. If there is an adverse condition associated with the pregnancy, the adverse condition is recorded on the AE eCRF page, but not the pregnancy itself. If an adverse condition as a result of pregnancy is considered serious, an SAE Form must be completed. All reports of congenital abnormalities / birth defects in the offspring of study participants are SAEs. Spontaneous miscarriages should also be reported and handled as SAEs.

Screening Failures

Subjects who are pregnant before study drug administration (and who will hence be screening failures) will not be followed up.

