3.9. Regulatory and Ethical Considerations

The study will be conducted in accordance with all applicable regulatory requirements.

This study will be conducted in compliance with the protocol approved by the relevant Independent Ethics Committee (IEC) / Institutional Review Board (IRB) and according to the Principles of the International Conference of Harmonisation (ICH) guidelines for Good Clinical Practice (GCP) E6(R1). In addition, it will be conducted in accordance with all local, federal and / or regional regulatory requirements and the principles which have their origin in the Declaration of Helsinki.

The Sponsor will obtain favourable opinion / approval to conduct the study from the appropriate regulatory agency, in accordance with applicable regulatory requirements, prior to a site initiating the study in that country.

Protocol waivers or exemptions are not allowed unless necessary to eliminate apparent immediate hazards to the subject. This should not normally arise in the context of inclusion / exclusion criteria, since the subject is not yet fully included in the study at that point in time. Adherence to the study design requirements, including those specified in the study plan / flowchart, the study visit intervals and the responsibilities of masked and unmasked study staff and need for certification (refer to [Table 6](#), [Table 7](#) and [Table 8](#)), are essential and required for study conduct.

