4.2.1. Withdrawal from Repeat Injection

A withdrawal from repeat injection refers to any subject who does not receive repeat injection(s) (ocriplasmin or sham). Subjects withdrawn from repeat injection(s) should not be withdrawn from the study and, apart from repeat injection-related procedures, should continue all scheduled study visits and procedures until the end of the study to ensure complete follow-up.

The following events should be assessed at Visit 4a (Day 28) and Visit 6a (Day 63), before repeat injection. If any of these events apply, no further injection(s) should be given. For events that are deemed to be temporary, the injection can be postponed, if this is feasible within the protocol-specified study visit interval (refer to [Table 7](#)).

- Severe intraocular inflammation associated with previous injection
- Active intraocular inflammation or infection in either eye at the time of repeat injection
- Any signs or symptoms of lens subluxation associated with previous injection
- Any condition associated with previous injection requiring surgical treatment (*e.g.* new macular hole, worsening of existing macular hole, retinal tear, retinal detachment, IOP increase)
- Persistent presence of subretinal fluid or inner segment / outer segment (IS / OS) junction changes with functional impairment, associated with previous injection, at the time of repeat injection

- Persistent complaint of dim vision, dark adaptation problems or impaired night vision, or afferent pupillary defect, associated with previous injection, at the time of repeat injection
- BCVA decrease \geq 15 letters from baseline or BCVA worse than 20/400, in the study eye, at the time of repeat injection
- Significant ocular trauma in the study eye at the time of repeat injection
- Any other intraocular injection since previous study injection
- Pregnancy
- Subject's individual treatment assignment has been unmasked (emergency unmasking, refer to [Section 3.6.2](#))

In addition, subjects may be withdrawn from repeat injection at any time at the discretion of the Investigator (*e.g.* based on significant abnormalities on ophthalmic examination or functional test associated with previous injection not listed above).

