5.4. Post-injection Phone Call

The masked Investigator / designee will make a scripted phone call to each subject 24-72 hours after the injection visit. Based on this phone call, the subject may be invited back for an unscheduled study visit as per the masked Investigator's clinical judgement.

For the phone script, please refer to [Appendix 2](#).

5.5. Visit 3 - Day 7

The following procedures will be performed:

- BCVA (ETDRS) –**both eyes**
- Colour vision (Roth 28-hue) – **study eye only** (only at sites where the Roth 28 Colour Test is available)
Not needed for subjects > 80 years of age or with a diagnosis of dyschromatopsia at baseline
- Full ophthalmic examination – **study eye only**
- SD-OCT (6mm) – **study eye only**
- Record concomitant medications / treatments / interventions (refer to [Section 6.4](#))
- (S)AE monitoring (refer to [Section 8.4](#))

All information must be recorded in the subject's eCRF.

5.6. Visit 4a – Day 28

The following procedures will be performed:

- Urine pregnancy test (for women of childbearing potential only)
- BCVA (ETDRS) –**both eyes**
- Colour vision (Roth 28-hue) – **study eye only** (only at sites where the Roth 28 Colour Test is available)
Not needed for subjects > 80 years of age or with a diagnosis of dyschromatopsia at baseline
- B-scan ultrasound – **study eye only**
- Full ophthalmic examination – **study eye only**
- SD-OCT (6mm) – **study eye only**
- SD-OCT (widefield) – **study eye only** (only at sites where this is available).
- Assess list of events that lead to withdrawal from repeat injection (refer to [Section 4.2.1](#))
- Record concomitant medications / treatments / interventions (refer to [Section 6.4](#))
- (S)AE monitoring (refer to [Section 8.4](#))

All information must be recorded in the subject's eCRF.

5.7. Visit 4b – Day 35

The following procedures will be performed:

- Treatment number allocation for repeat injection (refer to [Section 3.5.2](#))
- Study treatment
- Post-injection assessment (IOP measurement and indirect ophthalmic examination)
The post-injection assessment should be performed by the unmasked treating investigator as many times as needed at his / her discretion but at least once within 60 minutes after the injection to exclude central retinal artery non-perfusion or other complications
- Record concomitant medications / treatments / interventions (refer to [Section 6.4](#))
- (S)AE monitoring (refer to [Section 8.4](#))

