5.8. Post-injection Phone Call

Refer to [Section 5.4](#).

5.9. Visit 5 –Day 42

The procedures to be performed at Visit 5 (Day 42) are the same as those to be performed at Visit 3 (Day 7). Refer to [Section 5.5](#) for the description of the study procedures at this visit.

5.10. Visit 6a – Day 63

The procedures to be performed at Visit 6a (Day 63) are the same as those to be performed at Visit 4a (Day 28). Refer to [Section 5.6](#) for the description of the study procedures at this visit.

5.11. Visit 6b – Day 70

The procedures to be performed at Visit 6b (Day 70) are the same as those to be performed at Visit 4b (Day 35). Refer to [Section 5.7](#) for the description of the study procedures at this visit.

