7.2.2. SD-OCT (6mm)

6mm SD-OCTs will be used for assessment of efficacy (total PVD, macular oedema) and safety. The images will be submitted to and evaluated by the masked CRC.

6mm SD-OCT imaging will be performed for all subjects:

- At Visit 1 (screening visit) for **potential study eye(s)**
If 1 of the subject's eyes is excluded based on an eligibility criterion that does not need confirmation by the B-scan expert reader or the CRC, no SD-OCT needs to be taken for that eye. If both eyes potentially qualify as the study eye, SD-OCT imaging needs to be performed for both eyes
- At each scheduled study visit, with the exception of Visit 2 (Day 0) and the repeat injection visits (Visit 4b [Day 35] and Visit 6b [Day 70]), for the **study eye**

7.2.3. 7-Standard Field Stereo Colour Fundus Photography

7-standard field stereo colour fundus photography will be used to assess DR stage, neovascularisation and vitreous / pre-retinal haemorrhage. The images will be submitted to and evaluated by the masked CRC.

7-standard field stereo colour fundus photographs will be taken for all subjects:

- At Visit 1 (screening visit) for **potential study eye(s)**
If 1 of the subject's eyes is excluded based on an eligibility criterion that does not need confirmation by the B-scan expert reader or the CRC, no 7-standard field stereo colour fundus photograph need to be taken for that eye. If both eyes potentially qualify as the study eye, 7-standard field stereo colour photographs need to be taken for both eyes
- At Visit 10 (Month 15) and at Visit 11 (Month 24) / the Exit Visit for the **study eye**

In addition, 7-standard field stereo colour fundus photographs will be taken for subjects that the Investigator suspects progressed to PDR:

- At Visit 8 (Month 3) and at Visit 9 (Month 9)

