Procedures indicated by ‘**T**’ should be performed by the unmasked treating investigator / designee. Procedures indicated by ‘**O**’ are optional. At Visit 8 (Month 3) and Visit 9 (Month 9), 7-standard field stereo colour fundus photographs should only be taken if the Investigator suspects that the subject has progressed to PDR. Light grey coloured visits indicate injection visits.

^a For screening failures due to reasons that are expected to be temporary, and for subjects for whom eligibility cannot be timely determined due to a problem with one of the eligibility assessments (e.g. in case of ungradable B-scan ultrasound), 1 re-screening visit can be organised. The re-screening visit should be scheduled at least 28 days after the 1st screening visit

^b The masked Investigator / designee will make a scripted phone call to each subject 24-72 hours after the injection visit. Based on this phone call, the subject may be invited back for an unscheduled study visit as per the masked Investigator’s clinical judgement

^c Only for women of childbearing potential. Serum pregnancy test at screening (Visit 1), urine pregnancy test at Visit 4a and Visit 6a. Urine pregnancy testing should be repeated in any woman of childbearing potential who missed 1 period

^d Performed in both eyes. Ophthalmic assessments without footnote are performed in the study eye only

^e Not needed for subjects > 80 years of age or with a diagnosis of dyschromatopsia at baseline

- ^f Only at sites where this is available
- ^g Performed in potential study eye(s) only. If one of the subject's eyes is excluded based on an eligibility criterion that does not need confirmation by the B-scan expert reader or the CRC, these examinations do not need to be performed for that eye. If both eyes potentially qualify as the study eye, these examinations need to be performed for both eyes
- ^h Full ophthalmic examination including pupillary examination, slit lamp examination, IOP assessment and dilated fundus examination. The same slit lamp machine should be used across study visits for a given subject
- ⁱ ffERG will be performed at sites where this is available, in approximately 25% of the subjects
- ^j Only for subjects with expert-defined ffERG abnormalities at the previous assessment
- ^k Refer to [Section 4.2.1](#) for the list of withdrawal criteria from repeat injection

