- ^l Randomisation can only occur after confirmation of eligibility by the B-scan expert reader, the CRC and the central laboratory
- ^m Post-injection IOP measurement and indirect ophthalmic examination will be performed by the unmasked treating investigator as many times as needed at his / her discretion but at least once within 60 minutes after the injection to exclude central retinal artery non-perfusion or other complications

Table 7: Study Visit Intervals

Interval	Optimal Interval	Allowed Interval
Visit 1 (Screening) → Visit 2 (Day 0)	10-14 days	10-17 days
Visit 2 → Post-injection Phone Call	24–48 hours	24–72 hours ^a
Visit 2 (Day 0) → Visit 3 (Day 7)	7 days	7±3 days (4–10 days)
Visit 2 (Day 0) → Visit 4a (Day 28)	28 days	28±3 days (25-31 days)
Visit 4a (Day 28) → Visit 4b (Day 35)	7 days	6-10 days
Visit 4b (Day 35) → Post-injection Phone Call	24–48 hours	24–72 hours ^a
Visit 4b (Day 35) → Visit 5 (Day 42)	7 days	7±3 days (4–10 days)
Visit 4b (Day 35) → Visit 6a (Day 63)	28 days	28±3days (25-31 days)
Visit 6a (Day 63) → Visit 6b (Day 70)	7 days	6-10 days
Visit 6b (Day 70) → Post-injection Phone Call	24–48 hours	24–72 hours ^a
Visit 6b (Day 70) → Visit 7 (Day 77)	7 days	7±3 days (4–10 days)
Visit 6b (Day 70) → Visit 8 (Day 98)	28 days	28±3days (25-31 days)
Visit 2 (Day 0) → Visit 9 (Month 9)	270 days	270±14 days (256-284 days)
Visit 2 (Day 0) → Visit 10 (Month 15)	450 days	450±14 days (436-464 days)
Visit 2 (Day 0) → Visit 11 (Month 24)	720 days	720±14 days (706-734 days)

^a If an unscheduled post-injection visit falls within the allowed interval for the 7-days post-injection visit (4-10 days after injection), the unscheduled post-injection visit and the Day 7 visit will take place on the same day

Table 8: Responsibilities Masked and Unmasked Study Staff and Need for Certification

Study Procedure	Masked Study Staff	Unmasked Study Staff	Certification needed
Study drug:			
Study drug accountability		X	
Injection-related procedures:			
IXRS access		X	
(Pre-)injection procedures		X	
1-hour post-injection assessment		X	
Scripted phone call 24-72 hours after the injection	X		
Conduct unscheduled study visit(s)	X		
Assess list of events that lead to withdrawal from repeat injection	X		
AE reporting:			
AEs during 1-hour post-injection assessment		X	
All other AEs	X		
Ophthalmic assessment:			
BCVA	X		
Colour vision (Roth 28-hue)	X		
B-scan ultrasound	X		X
Full ophthalmic examination	X		
7-standard field stereo colour fundus photography	X		X

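### Section 8.4.2 requires a urine pregnancy test at each repeat injection visit (4b and 6b), but the schedule places it only at Visits 4a and 6a, 6-10 days before the injection

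*Protocol*

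**What the plan says.** Section 8.4.2 requires negative pregnancy tests at Visits 1 and 2. For the later injections it states that "a urine pregnancy test will be taken at each repeat injection visit", and it adds a test for any woman of childbearing potential who misses a period. It also bars further injection of a woman who is pregnant when the repeat injection is due.

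The term has a settled meaning in the protocol. Section 7.2.2 refers to "the repeat injection visits (Visit 4b [Day 35] and Visit 6b [Day 70", and Sections 7.2.5 and 8.2.4 name the same two visits.

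The schedule differs. The list for Visit 4b in Section 5.7 opens with "Treatment number allocation for repeat injection" and has no pregnancy test. Section 5.11 then says: "The procedures to be performed at Visit 6b (Day 70) are the same as those to be performed at Visit 4b (Day 35". The test appears in the list for Visit 4a (Section 5.6), which Visit 6a repeats (Section 5.10). Footnote c of Table 6 places the "urine pregnancy test at Visit 4a and Visit 6a".

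Pregnancy is also one of the events in Section 4.2.1 that stop further injections. That section says: "The following events should be assessed at Visit 4a (Day 28) and Visit 6a (Day 63), before repeat injection".

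**The concern.** A site cannot meet Section 8.4.2 by working through the visit lists or the flowchart. Section 3.9 declares essential "Adherence to the study design requirements, including those specified in the study plan / flowchart", so a site working from Table 6 may well leave out the test that Section 8.4.2 demands.

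What is at stake is a dosing safeguard. The rule against injecting a pregnant subject applies when the injection is given, but the scheduled evidence for it comes from an earlier visit. The first injection is treated more strictly: Section 5.2 has a serum test at screening and Section 5.3 repeats the check with a urine test at Visit 2, although Table 7 puts those visits only 10-17 days apart. The two repeat injections have no such second check. No efficacy or safety estimate depends on this point.

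**Working it through.** There is no sample size, power or error-rate figure to reproduce. The check sets the texts side by side and then reads the intervals from Table 7.

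**Which visits are meant.** Sections 7.2.2, 7.2.5 and 8.2.4 all name 4b and 6b as the repeat injection visits. The introduction to Section 5 counts three injection visits, which fits Visits 2, 4b and 6b.

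**Where the test is required and where it is scheduled.**

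| Visit | Section 8.4.2 | Visit list | Table 6, pregnancy test row |
|---|---|---|---|
| 2 (Day 0), injection | required | urine test (5.3) | marked |
| 4a (Day 28) | not named | urine test (5.6) | marked |
| 4b (Day 35), injection | required | none (5.7) | not marked |
| 6a (Day 63) | not named | urine test (5.10, as 5.6) | marked |
| 6b (Day 70), injection | required | none (5.11, as 5.7) | not marked |

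Section 5.7 has five items: treatment number allocation, study treatment, post-injection assessment, concomitant medications and adverse event monitoring. None is a pregnancy check.

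**Age of the scheduled test at the repeat injection.**
- Nominal: 35 - 28 = 7 days, and 70 - 63 = 7 days.
- Allowed for the first repeat injection, from Table 7: "Visit 4a (Day 28) → Visit 4b (Day 35) 7 days 6-10 days", that is, 6-10 days.
- Allowed for the second repeat injection (6a to 6b): also 6-10 days.
- At Visit 2 the urine test belongs to the injection visit itself.

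**Whether a 4a test could double as a same-visit test.** It could not. Section 3.5.2 lets repeat treatment be allocated only after the masked readers have assessed total PVD status, and Table 7 sets at least 6 days between the two visits.

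**Interval between scheduled tests.** Table 7 allows 25-31 days from 4b to 6a. The 4a and 6a tests are therefore (6 + 25) to (10 + 31) = 31-41 days apart. This is context only; the contradiction does not depend on it.

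**Who could be exposed.** Repeat drug is possible only in the ocriplasmin arms, 46 + 46 = 92 of 115 planned subjects, and there only in subjects without total PVD; the others receive sham. The count of 92 covers both sexes and all ages, so it is a loose upper bound. The protocol's clarification note reports 48 randomised. If the 2:2:1 ratio held (an assumption), the bound falls to 48 × 4/5 ≈ 38.

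**The case against.** The strongest reply is that one sentence in Section 8.4.2 is the outlier and the rest of the schedule is coherent. Sections 5.6 and 5.10, Table 6, footnote c and Section 4.2.1 all put the pregnancy check at 4a and 6a. Section 4.2.1 also words several criteria as applying when the repeat injection is given, yet has them assessed at 4a and 6a. One is a visual acuity loss of 15 letters or more, and Section 7.2.5 does not measure acuity at 4b or 6b. The dosing rule in Section 8.4.2 could be read in the same loose way. That has some force for the dosing rule. It does not rescue the testing requirement, which names a kind of visit that the protocol defines as 4b and 6b.

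Section 3.9 requires compliance with the whole protocol and does not rank the flowchart above Section 8.4.2. A site could satisfy both by testing at 4b and 6b as well. Omission is therefore a likely result of the schedule, not a certain one.

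Other safeguards exist: mandatory contraception, a test after a missed period, and pregnancy as a reason to stop injections. They lower the risk, but none is a scheduled check at 4b or 6b.

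Finally, rewording Section 8.4.2 to name Visits 4a and 6a would also remove the contradiction, at no burden to subjects, and the documents do not show that a same-visit test is necessary. This is a fair alternative. Its drawback is that it lowers a safeguard the protocol already states.

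**Conclusion.** The concern holds. Section 8.4.2 requires a urine test at Visits 4b and 6b, and neither the visit lists nor the flowchart provides one. As scheduled, the test is 6-10 days old at each of up to two repeat injections, against a test at the injection visit itself for the first.

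This conclusion rests on the protocol's own use of the term for the repeat injection visits and on the Table 7 windows. The number of women of childbearing potential is not stated, so no exposure risk can be computed, and the early end of recruitment limits how many could have been affected. The matter is an internal inconsistency in a safety procedure. It should be corrected, and it does not bear on the analysis.

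**What to change.** Add a urine pregnancy test for women of childbearing potential, before treatment number allocation, to the Visit 4b list in Section 5.7. Section 5.11 then carries it to Visit 6b. Mark V4b and V6b in the Table 6 pregnancy test row and name both visits in footnote c. Keep the tests at 4a and 6a, because they support the withdrawal assessment in Section 4.2.1.

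The cost is one urine test per woman at each of two visits already scheduled, plus the wording changes. Table 8 lets masked or unmasked staff do urine pregnancy tests, so masking is unaffected.

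If the sponsor judges the earlier test sufficient, the alternative is to change Section 8.4.2 to name Visits 4a and 6a and say why. That restores consistency but gives up the check at the injection visit.
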